3.3 Curcumin

3.3.1 Description

Curcumin (Diferuloylmethane) is a naturally occurring polyphenol, the active ingredient in the dried ground rhizome of the perennial herb *Curcuma longa*, commonly known as turmeric. Turmeric has universal appeal as a colouring agent, food preservative and flavouring agent in foods. Over the past three decades, it has been studied as an antioxidant, anti-inflammatory, cancer chemopreventive and potentially as a chemotherapeutic agent.

The chemical name for curcumin is [1,7-bis-(4-hydroxy-3-methoxyphenyl)-1,6-heptadiene-3,5-dione]. This bis-unsaturated-diketone exists in equilibrium with its enol tautomer. Curcumin has a molecular weight of 368.37 and the following structural formula:

Curcumin is an orange-yellow crystalline powder that is insoluble in water but

soluble in acetone, alcohol and glacial acetic acid.

Drug Formulation, Packaging, and Storage

Curcumin is available as 1 gm capsules of C3Complex (Sabinsa Corporation, New Jersey). This consists of standardized extract of phenolic compounds from turmeric root (*Curcuma longa* fam. Zingiberaceae) containing high purity curcuminoids (minimum 95% by HPLC). Curcuminoids include 2.5-6.5% bisdemethoxy-curcumin, 15-25% demethoxy- curcumin, and 70-80% curcumin. *Curcuma longa* is listed in the FDA' GRAS list, a list of food additives which are "Generally Recognized As Safe" by a consensus of scientific opinion. The GRAS list appears in the Code of Federal Regulations (CFR) Title 21 Parts 172, 182, 184 and 186. C3Complex should be stored at room temperature 25° C (77° F) [excursions permitted to 15-30° C (59-86° F] in the container in which they are provided.

3.3.2 Adverse Events

Incidence rates of adverse events associated with curcumin are rare. The following events may be expected with the administration of curcumin:

- 3.3.3.1 Gastrointestinal: Occasional mild diarrhea has been noted in some human subjects .
- 3.3.3.2 Hematologic: None expected.
- 3.3.3.3 Hepatic: None expected
- 3.3.3.4 Renal: None expected
- 3.3.3.5 Respiratory: None expected
- 3.3.3.6 Anaphylactic-like reactions:.. No cases of anaphylactic reactions and/or angioedema have been reported in patients receiving curcumin.
- 3.3.3.7 Neurological: None expected
- 3.3.3.8 General: None expected

3.3.3 Drug Interactions: None known.

3.3.4 Contraindications: Curcumin is contraindicated in patients with hypersensitivities to curcumin.

3.3.5 Clinical studies:

In an early report from 1987, Kuttan reported on turmeric as a topical treatment for oral cancers and leukoplakia (82). This research group reported a reduction in the size of the lesions in 10% of the 62 patients treated. The study was limited by the lack of a control group, no assessment of anti-inflammatory activity and no chemical analysis of the preparation applied. Nonetheless, the results suggest the potential for antineoplastic properties.

A phase I trial evaluated the pharmacokinetics of curcumin in Taiwanese subjects with a variety of "high risk or pre-malignant" lesions such as oral leukoplakia and cervical intraepithelial neoplasia among others (83). The starting oral dose was 500 mg a day and this was escalated to 12,000 mg. No treatment related toxicity was observed. There was a dose related increase in measured plasma levels. Of

the seven patients with leukoplakia, 2 showed histologic improvement, although progression was observed in one. In total, 7 of 25 patients enrolled showed some degree of histologic improvement.

A recent phase 1 study evaluated a curcuminoid formulation in healthy volunteers using a single dose of standardized powder extract, uniformly milled curcumin. Doses were escalated from 0.5 to 12 gm and only minimal toxicity was noted and it did not appear to dose-related. The observed adverse events included diarrhea, headache, rash, and yellow stool. Low levels of curcumin were detected in the serum in 2 subjects who received >8gm (84).

A phase I study was completed at the University of Leicester in England using 15 subjects with advanced colorectal cancers (85, 86). The subjects orally consumed curcumin doses of 450 mg up to 3.6 gm daily for up to 4 months. Two patients experienced mild diarrhea, but there was no dose limiting toxicity observed. Three indices of potential pharmacological activity of curcumin were evaluated (based on preclinical data). These were GST activity, levels of a deoxyguanosine adduct (M1G) (which is related to oxidative stress and can be altered by curcumin in the diet of animals or human subjects), and prostaglandin levels as an indicator of COX-2 activity. Curcumin consumed at 3.6 gm levels generated detectable levels of parent compound and conjugates in plasma and urine, demonstrating bioavailability outside the gastrointestinal tract. The same dose caused inhibition of PGE2 production in blood leukocytes (measured ex vivo). Therefore the authors concluded that 3.6 gm was a suitable oral dose for evaluation of phase II trials. In addition, since the measurement of compliance is important in the context of intervention trials, the consistent presence of curcumin and its conjugates in urine observed in patients consuming 3.6 gm of curcumin daily is of potential relevance to the use of curcumin as a chemopreventive agent.

In another study evaluating human pharmacokinetics, twelve patients with confirmed colorectal cancer received oral curcumin at 0.45, 1.8 or 3.6 gm per diem for 7 days prior to surgery (87). Levels of agent-derived species were determined in the peripheral circulation and in colorectal tissue obtained at the time of surgical resection. The concentrations of curcumin in normal and malignant colorectal tissue of patients consuming 3.6 g daily of curcumin were 12.7 ± 5.7 and 7.7 ± 1.8 nmol/gm tissue, respectively. Curcumin sulphate and curcumin glucuronide were identified in the intestinal tissues of these patients. Trace levels of curcumin were found in the peripheral circulation. Compatible with the preclinical data presented above, these results also suggest that a daily dose of 3.6 gm curcumin achieves relatively high levels in colorectal tissue with measurable distribution of the parent drug outside the gut.

4.0 Patient Eligibility

4.1 Inclusion Criteria

- 4.1.1. All patients must have clinical stage T3,4 N0,1,2 or T2N1,2 adenocarcinoma of the rectum. Patients will be clinically staged using endorectal ultrasound, pelvic CT or MRI, and physical examination.
- 4.1.2. Histology must be confirmed with review by the Department of Pathology at MDACC.
- 4.1.3. All patients must have no distant metastatic disease in the liver, peritoneum, lungs, or paraaortic lymph nodes.
- 4.1.4. Patients must have a performance status (Karnofsky scale) of 70% or greater.
- 4.1.5. Patients must be \geq 18 years of age.
- 4.1.6. Patients must have ANC > 1200 cells/mm³, platelets $> 100,000$ /mm³, total serum bilirubin < 2 mg/dl, BUN < 30 mg/dl, creatinine < 1.5 mg/dl or creatinine clearance > 50 cc/min (estimated as calculated with Cockcroft-Gault equation).

Creatinine Clearance (men) = $\{(140 - \text{age}) \times \text{lean body weight (in kg.)}\} / \{\text{Plasma creatinine (mg/dl)} \times 72\}$

Creatinine Clearance (women) = $0.85 \times \{(140 - \text{age}) \times \text{lean body weight (in kg.)}\} / \{\text{Plasma creatinine (mg/dl)} \times 72\}$
- 4.1.7. Patients must have signed informed consent indicating that they are aware of the investigational nature of the study, and are aware that participation is voluntary. Patients must also agree to refrain from use of additional herbal supplements during the course of the study.
- 4.1.8. Postmenopausal woman must have been amenorrheic for at least 12 months to be considered of non-childbearing potential. Patients will agree to continue contraception for 30 days from the date of the last study drug administration. Sexually active males must practice contraception during the study.

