Capecitabine is contraindicated in patients with severe renal impairment (creatinine clearance below 30 mL/min [Cockroft and Gault]). In patients with moderate renal impairment (creatinine clearance 30-50 mL/min [Cockroft and Gault]) at baseline, a dose reduction to 75% of the Capecitabine starting dose is recommended. In patients with mild renal impairment (creatinine clearance 51-80 mL/min) no adjustment in starting dose is recommended.

Cockroft and Gault Equation:

$$\text{Creatinine clearance for males} = \frac{(140 - \text{age [yrs]}) (\text{body wt [kg]})}{(72) (\text{serum creatinine [mg/dL]})}$$

Creatinine clearance for females = 0.85 x male value

Following oral administration of 1250 mg/m² capecitabine twice a day to cancer patients with varying degrees of renal impairment, patients with moderate (creatinine clearance = 30-50 mL/min) and severe (creatinine clearance <30 mL/min) renal impairment showed 85% and 258% higher systemic exposure to FBAL on day 1 compared to normal renal function patients (creatinine clearance >80 mL/min). Systemic exposure to 5'-DFUR was 42% and 71% greater in moderately and severely renal impaired patients, respectively, than in normal patients. Systemic exposure to capecitabine was about 25% greater in both moderately and severely renal impaired patients.

3.2.9.3 Hand-Foot Syndrome:

Hand-Foot Syndrome: Hand-foot syndrome (palmar-plantar erythrodysesthesia or chemotherapy induced acral erythema) is a cutaneous toxicity (median time to onset of 79 days, range from 11 to 360 days) with a severity range of grades 1 to 3. Grade 1 is characterized by any of the following: numbness, dysesthesia/paresthesia, tingling,

painless swelling or erythema of the hands and/or feet and/or discomfort which does not disrupt normal activities. Grade 2 hand-and-foot syndrome is defined as painful erythema and swelling of the hands and/or feet and/or discomfort affecting the patient's activities of daily living. Grade 3 hand-and-foot syndrome is defined as moist desquamation, ulceration, blistering or severe pain of the hands and/or feet and/or severe discomfort that causes the patient to be unable to work or perform activities of daily living. If grade 2 or 3 hand-and-foot syndrome occurs, administration of capecitabine should be interrupted until the event resolves or decreases in intensity to grade 1. Following grade 3 hand-and-foot syndrome, subsequent doses of capecitabine should be decreased.

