4.2 Exclusion Criteria

- 4.2.1. Prior complete course up to 5 Gy of radiotherapy to the pelvis.
- 4.2.2. Pregnant or lactating woman. Women of childbearing potential who have not undergone a hysterectomy with either a positive or no pregnancy test at baseline. Women / men of childbearing potential not using a reliable and appropriate contraceptive method (oral, injectable, or implantable hormonal contraceptive; tubal ligation; intra-uterine device; barrier contraceptive with spermicide; or vasectomized partner).
- 4.2.3. Treatment for other carcinomas within the last five years, except cured

non-melanoma skin and treated in-situ cervical cancer.

[figure not shown]
- 4.2.4 Patients with uncontrolled intercurrent illness including, but not limited to, ongoing or requiring IV antibiotics, cardiac disease NYHA class III or IV, unstable angina pectoris, unstable cardiac arrhythmia or tachycardia (heart rate > 100 beats/minute), or psychiatric illness/ social situations that would limit compliance with the study requirements are excluded.
- 4.2.5 Other serious uncontrolled medical conditions that the investigator feels might compromise study participation.
- 4.2.6 Major surgery within 4 weeks of the start of study treatment.
- 4.2.7 Prior unanticipated severe reaction to fluoropyrimidine therapy or known hypersensitivity to 5-fluorouracil or capecitabine or curcumin.
- 4.2.8 Concurrent use of coumadin other than low dose (1 mg) coumadin used for line patency. Patients on coumadin must be changed to Lovenox at least 1 week prior to starting capecitabine.
- 4.2.9 Concurrent use of cimetidine, allopurinol, or aluminium hydroxide and magnesium hydroxide-containing antacids such as Maalox.
- 4.2.10 Sorivudine and brivudine use within 4 weeks of the start of study treatment.

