5.3.1.1 Cautions when used with other medications

5.3.1.1.1 Concurrent use of coumadin other than low dose (1 mg) coumadin used for line patency is contraindicated. Patients on coumadin must be changed to Lovenox at least 1 week prior to starting capecitabine.

5.3.1.1.2 Increased phenytoin plasma concentrations have been reported during concomitant use of Capecitabine with phenytoin, suggesting a potential interaction. Patients taking phenytoin concomitantly with Capecitabine should be monitored weekly for increased phenytoin plasma concentrations and associated clinical symptoms.

5.3.1.1.3 Allopurinol. Oxpurinol, a metabolite of allopurinol, can potentially interfere with 5-FU anabolism via orotate phosphoribosyltransferase. Although this was originally used as a strategy to protect normal tissues from 5-FU-associated toxicity, further laboratory studies suggested possible antagonism of the anticancer activity of 5-FU in some tumor models. If a patient is receiving allopurinol, the need for taking this medicine should be ascertained. If possible, allopurinol should be discontinued prior to starting on this regimen, and another agent substituted for it.

5.3.1.1.4 Cimetidine: Because cimetidine can decrease the clearance of 5-FU, patients should not enter on this study until the cimetidine is discontinued. Ranitidine or a drug from another anti-ulcer class can be substituted for cimetidine if necessary.

5.3.1.1.5 Sorivudine and Brivudine: A metabolite of the above two investigational antiviral agents, 5-bromovinyluracil, is a potent inhibitor of dihydropyrimidine dehydrogenase, the enzyme that catabolizes 5-FU. Patients should not receive concurrent therapy with either of these antiviral agents while receiving capecitabine. If a patient has received prior sorivudine or brivudine, then at least four weeks must elapse before the patient receives capecitabine therapy.

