5.3.1.5 Warnings and Precautions

5.3.1.5.1 **Renal Insufficiency:** Patients with moderate renal impairment at baseline require dose reduction (See section 3.2.9.2, Dosage Regimen and Administration.) Patients with mild and moderate renal impairment at baseline should be carefully monitored for adverse events. Prompt interruption of therapy with subsequent dose adjustments will be made if a patient develops a grade 2 to 4 adverse event. Patients will be taken off study if they do not recover. Capecitabine is contraindicated in patients with a creatinine clearance of < 30 ml/min.

5.3.1.5.2 **Pregnancy/Nursing:** Capecitabine may cause fetal harm when given to a pregnant woman. If the drug is used during pregnancy, or if the patient becomes pregnant while receiving this drug, the patient should be apprised of the potential hazard to the fetus. Women of childbearing potential should be advised to avoid becoming pregnant while receiving treatment with capecitabine. Because of the potential for serious adverse reactions in nursing infants from capecitabine, it is recommended that nursing be discontinued when receiving capecitabine therapy.

5.3.1.5.3 **Coagulopathy:** Patients receiving concomitant capecitabine and oral coumarin-derivative anticoagulant therapy should have their anticoagulant response (INR or prothrombin time) monitored frequently in order to adjust the anticoagulant dose accordingly. A clinically important Capecitabine-Warfarin drug interaction was demonstrated in a clinical pharmacology trial. Altered coagulation parameters and/or bleeding, including death, have been reported in patients taking capecitabine concomitantly with coumarin-derivative

anticoagulants such as warfarin and phenprocoumon. Postmarketing reports have shown clinically significant increases in prothrombin time (PT) and INR in patients who were stabilized on anticoagulants at the time capecitabine was introduced. These events occurred within several days and up to several months after initiating capecitabine therapy and, in a few cases, within one month after stopping capecitabine. These events occurred in patients with and without liver metastases. Age greater than 60 and a diagnosis of cancer independently predispose patients to an increased risk of coagulopathy.

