10.1 Off-study criteria

Patients who have documented clinical progression of disease that is discovered upon symptomatic progression during therapy will be taken off study. Patients will be taken off study if they fail to complete protocol therapy for reasons other than treatment related toxicity or tumor progression and will not be counted in the analysis. Patients will be taken off study if they miss two consecutive appointments.

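### The renal entry rule sets no minimum creatinine clearance for patients who enter on serum creatinine, so a patient who cannot be given capecitabine can be randomised

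*Combined protocol and SAP*

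**What the plan says.** Criterion 4.1.6 sets the renal requirement as "creatinine < 1.5 mg/dl or creatinine clearance > 50 cc/min", alongside BUN below 30 mg/dl. Its clearance is a Cockcroft-Gault estimate using lean body weight. Section 4.1 has a minimum age of 18 but no upper age limit and no minimum weight. Section 4.2 has no renal threshold; 4.2.5 leaves other serious uncontrolled conditions to the investigator's judgement.

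The drug background (3.2.9.2, printed under 3.1.9 Special Populations) states: "Capecitabine is contraindicated in patients with severe renal impairment (creatinine clearance below 30 mL/min". For clearance of 30-50 mL/min it says that "a dose reduction to 75% of the Capecitabine starting dose is recommended". The treatment section repeats both rules in 5.3.1.5.1: "Capecitabine is contraindicated in patients with a creatinine clearance of < 30 ml/min" and "Patients with moderate renal impairment at baseline require dose reduction".

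The pretreatment list in 6.1.1.1 includes serum creatinine. Neither that list nor the study calendar in 7.12 includes a clearance calculation.

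Section 10.1 removes from the study those who "fail to complete protocol therapy for reasons other than treatment related toxicity or tumor progression and will not be counted in the analysis".

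**The concern.** The entry rule and the treatment rule use different measures. Entry can rest on serum creatinine alone, whereas the contraindication is defined by clearance, which also depends on age, weight and sex. In an older, light patient a creatinine below 1.5 mg/dl can go with a clearance below 30 mL/min.

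The main harm is an avoidable randomisation. The patient is assigned to an arm and then cannot receive the drug that both arms share. Curcumin or placebo is also tied to capecitabine, since 5.4 stops it whenever capecitabine is discontinued. Impairment present at baseline is neither treatment-related toxicity nor progression, so 10.1 may remove the patient from the analysis after randomisation. Contraindicated dosing would follow only if 5.3.1.5.1 were overlooked.

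The protocol treats another capecitabine contraindication differently. Section 5.3.1.1.1 says "Concurrent use of coumadin other than low dose (1 mg) coumadin used for line patency is contraindicated", and exclusion 4.2.8 carries it into eligibility: "Concurrent use of coumadin other than low dose (1 mg) coumadin used for line patency". The clearance limit of 30 mL/min is not carried over in this way.

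**Working it through.** The plan gives no figure of its own to reproduce here. The question is whether a patient can satisfy 4.1.6 and still fall below 30 mL/min.

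**Inputs from the documents**
- Entry on the creatinine limb: creatinine < 1.5 mg/dl (4.1.6).
- Contraindication: clearance < 30 mL/min (3.2.9.2 and 5.3.1.5.1).
- Formula in 3.2.9.2: clearance = (140 − age) × weight in kg / (72 × creatinine), multiplied by 0.85 for women.
- Arm sizes: 30 curcumin, 15 placebo (13.0).

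**Assumed inputs.** The documents give no distribution of age, weight or creatinine, so the patient profiles below are assumptions. I used body weight, as 3.2.9.2 does. The lean weight in 4.1.6 would give the same or a lower clearance, so this choice does not favour the finding.

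**Two example patients, creatinine 1.4 mg/dl**
- Woman aged 75, 50 kg: (65 × 50) / (72 × 1.4) × 0.85 = 3250 / 100.8 × 0.85 = 27.4 mL/min.
- Man aged 80, 50 kg: (60 × 50) / (72 × 1.4) = 3000 / 100.8 = 29.8 mL/min.

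Both satisfy the renal limb of 4.1.6, and capecitabine is contraindicated for both.

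**Weight below which clearance is under 30.** Setting clearance to 30 and solving for weight gives:
- Women: 30 × 72 × creatinine / (0.85 × (140 − age)).
- Men: 30 × 72 × creatinine / (140 − age).

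For example, a woman of 75 with creatinine 1.4: 3024 / (0.85 × 65) = 54.7 kg.

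| Creatinine (mg/dl) | Women aged 70 / 75 / 80 (kg) | Men aged 70 / 75 / 80 (kg) |
|---|---|---|
| 1.4 | 50.8 / 54.7 / 59.3 | 43.2 / 46.5 / 50.4 |
| 1.2 | 43.6 / 46.9 / 50.8 | 37.0 / 39.9 / 43.2 |
| 1.0 | 36.3 / 39.1 / 42.4 | 30.9 / 33.2 / 36.0 |

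The gap is therefore mainly for older, light patients, more often women, with creatinine near the limit. At 1.0 mg/dl the weights needed are very low.

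**What one patient represents.** 1/30 = 3.3% of the curcumin arm; 1/15 = 6.7% of the placebo arm.

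**Whether another step must catch it before randomisation.** Section 5.3.1.5.1 requires a dose reduction for moderate impairment at baseline, and 3.2.9.2 defines the grades by clearance. A site following both must know clearance before the first dose, but no text requires it before randomisation. The dosing paragraph 5.3.1 sends the reader to 5.3.1.3 for adjustments; that section covers toxicity on treatment and has no baseline renal rule.

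**The case against.** The strongest reply is that patients are already protected. Section 5.3.1.5.1 bars the drug below 30 mL/min, and its baseline dose-reduction rule means a careful site will calculate clearance before dosing. Creatinine is collected before enrolment, and 4.1.6 prints the formula. BUN below 30 mg/dl, Karnofsky of at least 70 and the discretionary exclusion 4.2.5 narrow the group further. All of this stands, and it limits the safety concern. It does not close the gap: the treatment rule acts on dosing rather than on randomisation, and none of the other criteria sets a clearance minimum.

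The analysis consequence can also be questioned. Section 13.0 counts patients treated with curcumin, so a patient never dosed may fall outside the 30, and applying 10.1 to someone who never started therapy is an inference. That is fair, and it is why the loss is described as possible. The protocol does not say how such a patient is handled. In addition, baseline clearance is fixed before assignment, so the assigned treatment does not cause the loss.

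Admitting patients at 30-50 mL/min is plainly intended, given the 75% starting dose, and is not criticised here. Nothing in the documents suggests that admitting patients below 30 was intended.

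**Conclusion.** The concern holds. Followed as written, 4.1.6 can admit a patient for whom the protocol contraindicates the drug common to both arms. That conclusion rests only on the text and the protocol's own formula.

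How often it would happen is unknown. Without age, weight and creatinine distributions no expected count can be computed, and the count may be zero. The 3.3% and 6.7% describe the weight of a single patient in each arm and are not estimates of frequency. The error rates, power and planned sample size of the design do not change. The correction is worth making because it prevents an avoidable post-randomisation problem in a trial of at most 45 patients at almost no cost.

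**What to change.** Add to 4.1.6 a requirement that every patient, whichever renal limb applies, has a Cockcroft-Gault clearance of at least 30 mL/min, using actual body weight with the 3.2.9.2 formula. Add to 6.1.1.1 that clearance is calculated from the screening creatinine before randomisation. Leave the 75% starting dose at 30-50 mL/min as it is.

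Stating the weight matters, because 3.2.9.2 says body weight while 4.1.6 uses lean weight. The two do not conflict: lean weight does not exceed actual weight, so anyone who qualifies on the limb above 50 is also above 30 by the new rule.

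The cost is two short edits. Creatinine is already required, and weight is already needed for dosing per m². The floor turns away only patients whom the protocol already bars from capecitabine.
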